| | B244 O.D. 5.0, B244 O.D. 20.0, Vehicle | XXXXXXX | | | Ongoing | | | | | | No |

 [1] WHO Drug Dictionary version YYYYMMM was used to code medication names.
 [2] Prior medication is defined as any medication with a stop date prior to the date of first dose of study drug. Source: SDTM.XXXX or ADaM.XXXX
 PROGRAM NAME: XXXXXXXXXX

DATE: HH:MM/DDMMMYYYY

Listing 16.2.13.2 Rescue Medications (Safety Population)

| | Treatment | Rescue Medication [1] | Date/ Time (Study Day) | Dose (Unit) | Route | Class |
|------------|--|-----------------------|---------------------------|-------------|-------|------------|
| Subject ID | | | | | | |
| XXXXXX | N/A, B244 O.D. 5.0, B244 O.D. 20.0, Vehicle | XXXXXXX | DDMMMYYYY/ HH:MM (xx) | xxx (xxx) | XXX | 4, 5, 6, 7 |

 [1] Rescue medications reported as "Other" in the ERT will be cross referenced with allowed rescue medications, prohibited medications, and concomitant medications (e.g., emollients, antihistamines, etc.) and only "Other" resuce medications that are on the allowed rescue medication list are included here.

 Source: SDTM.XXXX or ADaM.XXXX
 DATE: HH:MM/DDMMMYYYY

Listing 16.2.13.3 Rescue Medication Days (Safety Population)

| Subject ID | Treatment | Study Population | Study Period | Rescue Medication Days [1,2] | More than Threshold [3] |
|------------|-----------------|------------------|-----------------|------------------------------|-------------------------|
| XXXXXX | N/A, | N/A, | Baseline, | XXX | Yes, No |
| | B244 O.D. 5.0, | Safety, | Weeks $1-2$, | | |
| | B244 O.D. 20.0, | mITT, | Weeks $3 - 4$, | | |
| | Vehicle | PP | Weeks $1 - 4$, | | |
| | | | Weeks $5-6$, | | |
| | | | Weeks $7 - 8$, | | |
| | | | Weeks 5 – 8 | | |

[1] Baseline rescue medication days = number of rescue medication days from Day -14 to Day -1.

Weeks 1 - 2 rescue medication days = number of rescue medication days from Day 1 to Day of Visit 3 - 1.

Weeks 3 - 4 rescue medication days = number of rescue medication days from Day of Visit 3 to Day of Visit 4 - 1.

Weeks 1 - 4 total rescue medication days = number of rescue medication days from Day 1 to Day of Visit 4 - 1.

Weeks 5-6 rescue medication days = number of rescue medication days from Day of Visit 4 to Day of Visit 4 + 13.

Weeks 7 - 8 rescue medication days = number of rescue medication days from Day of Visit 4 + 14 to Day of Visit 5 - 1.

Weeks 5-8 total rescue medication days = number of rescue medication days from Day of Visit 4 to Day of Visit 5-1.

[2] Each time interval is normalized as a rate where (# Rescue Medication Days) = [(# Days Rescue Medications Used in Interval) / (# Actual Days in Interval)] * (# Expected Days in Interval).

[3] Rescue medication thresholds: ≤ 3 days in washout period (baseline), ≤ 7 days during Weeks 1 - 4, ≤ 7 days during Weeks 5 - 8.

Source: SDTM.XXXX or ADaM.XXXX

PROGRAM NAME: XXXXXXXXXX

DATE: HH:MM/DDMMMYYYY

Programming Notes:

• More than Threshold column should be populated for Study Periods: Baseline, Weeks 1 – 4, and Weeks 5 – 8.

Listing 16.2.14 Medical History (Safety Population)

| Subject ID | Treatment | Preferred Term [1] | MH # | Start Date | End Date/Ongoing | Current Treatment | CM # |
|---------------|--|----------------------------------|-----------|------------|-----------------------|-------------------|------|
| XXXXXX | N/A, B244 O.D. 5.0, B244 O.D. 20.0, Vehicle | xxxxxxx/ xxxxxxxx | XXX | DDMMMYYYY | DDMMMYYYY, Ongoing | Yes, No | XXX |
| [1] MedDRA Di | ictionary version XX.X w | vas used to code medical history | v events. | | | | |

Source: SDTM.XXXX or ADaM.XXXX PROGRAM NAME: XXXXXXXXXX

DATE: HH:MM/DDMMMYYYY

Listing 16.2.15.1 COVID-19 Test Results (Safety Population)

| Subject ID | Treatment | Test Date | COVID-19 Test | Test Type [1] | Result Type [2] | Result | Medically Confirmed |
|-------------------|--|----------------------------|--|-----------------|-----------------|-----------------------|------------------------|
| XXXXXX | N/A, B244 O.D. 5.0, B244 O.D. 20.0, Vehicle | DDMMMYYYY | Antibody, Viral, Other (specify) | Antigen, RNA | IgM, IgG | Positive, Negative | Yes, No |
| [1] Test type she | ould only be populated fo | r the Viral COVID-19 test. | | | | | |
| [2] Result type s | should only be populated | for the Antibody COVID-1 | 19 test. | | | | |
| Source: SDTM. | XXXX or ADaM.XXXX | | | | | | |
| PROGRAM NA | ME: XXXXXXXXXX | | | | | DATE: H | H:MM/DDMMMYYYY |

Listing 16.2.15.2 COVID-19 Missed Assessments (Safety Population)

| Subject ID | Treatment | Affected Visit | Assessments Not Done | Reason Not Done |
|------------|-----------------|----------------|----------------------------|--|
| XXXXXX | N/A, | Screening, | eDiary Review, | Site Closure, |
| | B244 O.D. 5.0, | Baseline, | IP Compliance, | Subject Decision (specify), |
| | B244 O.D. 20.0, | Week 2, | IP Dispensation, | Subject Decision – Over 60, |
| | Vehicle | Week 4, | Application of Study Drug, | Subject Decision – Underlying Health Issues, |
| | | Week 8 | Etc. | Etc. |
| | | | | |

Source: SDTM.XXXX or ADaM.XXXX PROGRAM NAME: XXXXXXXXXX

DATE: HH:MM/DDMMMYYYY

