APPENDIX C: EASI SCORE

How to Use EASI

The EASI scoring system uses a **defined process** to grade the **severity of the signs** of eczema and the **extent affected**:

1. Select a body region

Four body regions are considered separately:

- Head and neck
- · Trunk (including the genital area)
- Upper extremities
- · Lower Extremities (including the buttocks)

2. Assess the extent of eczema in that body region

Each body region has potentially 100% involvement. Using the table below, give each respective body region a score of between 0 and 6 based on the percentage involvement. Precise measurements are not required.

% involvement	0	1-9%	10 - 29%	30 - 49%	50 - 69%	70 - 89%	90 - 100%
Region score	0	1	2	3	4	5	6

To aid in your body region grading you can use the diagrams in Appendix 1.

Assess the severity of each of the four signs in that body region:

- 1. Erythema
- 2. Edema/papulation
- 3. Excoriation
- 4. Lichenification

Further explanations of these terms can be found in FAQ's (Appendix 4)

Grade the severity of each sign on a scale of 0 to 3:

0	None
1	Mild
2	Moderate
3	Severe

- Take an average of the severity across the involved region.
- ✓ Half points may be used e.g. 2.5.
- ✓ Palpation may be useful in assessing edema/papulation as well as lichenification

To aid your severity grading, a photographic atlas of suggested categories is available in Appendix 2

Remember: Include only inflamed areas in your assessment; do not include xerosis (dryness), ichthyosis, keratosis pilaris, urticaria, infection (unless there is underlying eczema), or post inflammatory pigmentation changes.

EASI guidance December 14

How to record your scores

The assessed parameters are inserted into a table (example shown below for age≥8 years). The final EASI score ranges from 0-72.

[figure not shown]
Body region	Erythema		Edema/ papulation	Excoriation	Lichenification	Area score	Multiplier	Score	
Head/neck	(+	+	+)	x	x0.1		
Trunk	(+	+	+)	x	× 0.3		
Upper extremities	(+	+	+)	x	x 0.2		
Lower extremities	(+	+	+)	x	x 0.4		
The final EASI score is the sum of the 4 region scores									

Two forms of the EASI scoring system are available depending on the age of the patients. The multipliers for the region score are different in the under 8's version to reflect the relative proportion of body regions in young children:

- Patients 8 years or above
- Patients under 8 years of age.

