The region scores, which reflect the extent of eczema, were designed and validated as rough estimates of the percentage of involved skin. Each region is given a score ranging from 0 to 6, based on a "ballpark" estimation of extent (see region score table in page 1). If you find it difficult to provide a rough estimate of disease extent, you can use the schematics in Appendix 1 to guide you. More time-consuming methods for evaluating disease extent such as the rule of nines or the 'palm' method are generally unnecessary, as the EASI was designed to be...easy.

My patient has responded well to treatment and significantly improved since the last visit. Should I adjust the grading based on the patient's relative improvement?

No. The EASI is a static score, meaning that it is done independently at each time point to reflect current severity. You should grade the EASI per visit regardless of the previous status. Studies have shown that the EASI score has good responsiveness, meaning that overall it is sensitive to change and the improvement will be reflected in the total score.

Can the EASI be used in children?

Yes. The EASI is performed in the same method in all age groups, but the calculation of the final EASI score differs by age. When calculating the EASI, each of the 4 region scores is multiplied by a constant which reflects the relative contribution of that region to the total body surface area. For patients 8 years and older the multipliers are 0.1 for the head/neck, 0.2 for the upper extremities, 0.3 for the trunk and 0.4 for the lower extremities. Below 8 years of age the head/neck multiplier is increased to 0.2 while the lower extremities multiplier decreases to 0.3, consistent with the proportions of these regions in childhood. Refer to Appendix 3 for EASI forms by age.

What happens if a child turns 8 during the course of the study? Which EASI formula should I use?

There are no clear-cut definitions for this situation. In general, if the study is a short term study such as an RCT lasting a few months — using the same formula throughout the trial is preferred, even if the child turns 8 during these months. Keeping the EASI formula consistent in this scenario can serve to preserve the EASI sensitivity to change (e.g. its change in response to treatment) without compromising the validity of the score.

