Listing 16.2.6.5 IGA (Randomized Subjects)

| Subject ID | Treatment | Study Population | Visit | Date of Rating | Rating [1] | Clear or Almost Clear | Any Improvement [2] | ≥2-Point Improvement to Clear or Almost Clear |
|------------|--|--------------------------------|---|----------------|---|-----------------------|---------------------|---|
| XXXXXX | N/A, B244 O.D. 5.0, B244 O.D. 20.0, Vehicle | N/A, Safety, mITT, PP | Screening, Baseline, Week 2, Week 4, Week 8 | DDMMMYYYY | Clear, Almost Clear, Mild, Moderate, Severe | Yes, No | Yes, No | Yes, No |

[1] Numeric item conversion: Clear=0; Almost Clear=1; Mild=2; Moderate=3; Severe=4.

[2] Any improvement is defined as \geq 1 point improvement from Baseline. Source: SDTM.XXXX or ADaM.XXXX

PROGRAM NAME: XXXXXXXXX

Listing 16.2.6.6 EASI Items and Score (Randomized Subjects)

| Subject ID | Tractmont | Study Bopulation | Visit | Data of Pating | Pody Area | EASI Itom | Dating [1] | Improvement |
|------------|-----------------|---------------------|------------|----------------|--------------------|---------------------|------------|--------------------|
| Subject ID | Treatment | Fopulation | VISIL | | Body Alea | EASI Itelli | | mprovement |
| XXXXXX | N/A, | N/A, | Screening, | DDMMMYYYY | Head/Neck, | Erythema | None, | Null if $< 50\%$, |
| | B244 O.D. 5.0, | Safety, | Baseline, | | Trunk, | Edema/Papulation | Mild, | ≥50%, |
| | B244 O.D. 20.0, | mITT, | Week 2, | | Upper Extremities, | Excoriation | Moderate, | ≥75% |
| | Vehicle | PP | Week 4, | | Lower Extremities, | Lichenification, | Severe, | ≥90% |
| | | | Week 8 | | | Area Score (%) [2], | xx-xx%, | |
| | | | | | Total | Total Score | XXX | |

[1] Numeric item conversion: None=0; Mild=1; Moderate=2; Severe=3.

[2] Numeric area score conversion: 1-9%=0; 10-29%=2; 30-49%=3; 50-69%=4; 70-89%=5; 90-100%=6.

Source: SDTM.XXXX or ADaM.XXXX

PROGRAM NAME: XXXXXXXXXX

DATE: HH:MM/DDMMMYYYY

Programming Notes:

• Body Area=Total corresponds to EASI Item=Total Score.

Listing 16.2.7.1 Adverse Events (Safety Population)

| Subject ID | Treatment | System Organ Class/ Preferred Term [1] | AE # | Start Date | End Date/Ongoing | Serious | SAE Criteria | Treatment Emergent | | |
|----------------------------------|---|---|------|------------|-----------------------|---------|--------------|-----------------------|--|--|

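### SAP Listing 16.2.6.6 converts 1–9% EASI involvement to an area score of 0 where Protocol Appendix C gives 1; if used in the derivation, this would usually overstate EASI improvement

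*SAP*

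**What the plan says.** Protocol Appendix C tells the assessor to "give each respective body region a score of between 0 and 6 based on the percentage involvement". The table beneath has two rows. The involvement bands are "involvement 0 1-9% 10 - 29% 30 - 49% 50 - 69% 70 - 89% 90 - 100" per cent, and the scores aligned with them are "Region score 0 1 2 3 4 5 6". So 0% scores 0 and 1–9% scores 1. The same table is printed on both case report forms in that appendix, and the FAQ confirms the range: "Each region is given a score ranging from 0 to 6".

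For SAP Listing 16.2.6.6 (EASI items and score), footnote 2 gives "Numeric area score conversion: 1-9%=0; 10-29%=2; 30-49%=3; 50-69%=4; 70-89%=5; 90-100%=6". The listing prints the area band, the EASI total and flags for improvement of at least 50%, 75% and 90%. SAP section 6.5.5 derives those flags from percent change in EASI. Section 7.7, which lists departures from the protocol's analyses, adds EASI responder endpoints but mentions no change to how EASI is scored.

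**The concern.** Five of the seven bands agree between the documents. The lowest two do not: the footnote gives 1–9% the score that belongs to 0%, leaves 0% out, and never uses 1. In the SAP text available for review, this footnote is the only place where an area band is turned into a number.

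If a program followed it, any region with residual eczema of 1–9% would be scored as clear. That would alter:

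- mean EASI change and the EASI-50, EASI-75 and EASI-90 rates (SAP 3.2.3 and 7.4);
- the SAP addendum's EASI tables (WOCF and LOCF mean change, LOCF EASI-75 and EASI-90);
- the baseline EASI strata of at most 10 and above 10 (SAP 7.4), which also subdivide the descriptive WI-NRS summaries.

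**Working it through.** **Inputs (Protocol Appendix C and its FAQ).** Severity: "Grade the severity of each sign on a scale of 0 to 3", for four signs, so a region's severity sum runs from 0 to 12. Weights for age 8 and over: "the multipliers are 0.1 for the head/neck, 0.2 for the upper extremities, 0.3 for the trunk and 0.4 for the lower extremities".

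**Formula.** EASI = sum over four regions of multiplier × severity sum × area score. Improvement = (baseline − follow-up) / baseline.

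**Check against the protocol's own figure.** The maximum is (0.1 + 0.3 + 0.2 + 0.4) × 12 × 6 = 72, which matches "The final EASI score ranges from 0-72". Both conversions give 72, so a range check on the derived data would not reveal the error.

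**The two conversions side by side.**

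| Involvement | Protocol | SAP footnote |
|---|---|---|
| 0% | 0 | no entry |
| 1–9% | 1 | 0 |
| 10–29% up to 90–100% | 2 to 6 | 2 to 6 |

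**Example 1: improvement overstated.** The head is clear. Trunk, upper and lower limbs go from 10–29% (severity sum 6) to 1–9% (severity sum 5). The three multipliers add to 0.9.

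- Baseline, both conversions: 0.9 × 6 × 2 = 10.8.
- Follow-up, protocol: 0.9 × 5 × 1 = 4.5. Improvement is 6.3 / 10.8 = 58.3%, which meets EASI-50 only.
- Follow-up, footnote: 0.9 × 5 × 0 = 0. Improvement is 100%, which meets EASI-50, EASI-75 and EASI-90 with eczema still present in three regions.

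**Example 2: improvement understated.** At baseline, head, trunk and upper limbs are at 1–9% and lower limbs at 10–29%, all with severity sum 6. At follow-up only the lower limbs remain, at 10–29% with severity sum 4.

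- Protocol: baseline 0.6 × 6 × 1 + 0.4 × 6 × 2 = 3.6 + 4.8 = 8.4. Follow-up is 0.4 × 4 × 2 = 3.2. Improvement is 5.2 / 8.4 = 61.9%.
- Footnote: baseline 4.8, follow-up 3.2. Improvement is 1.6 / 4.8 = 33.3%, and the EASI-50 response is lost.

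**Example 3: no effect.** If no region is at 1–9% at either visit, the two conversions agree. With three regions staying at 10–29% and severity sums falling from 6 to 2, both give 10.8 to 3.6, a 66.7% improvement.

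**Example 4: baseline stratum.** Trunk at 10–29% (severity sum 8), lower limbs at 10–29% (6) and upper limbs at 1–9% (6). The protocol gives 4.8 + 4.8 + 1.2 = 10.8; the footnote gives 9.6. The subject moves from the stratum above 10 to the other one.

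**Net direction (illustration only).** The documents give total affected BSA of 10–40% at entry but no regional extents, so these distributions are assumptions. Regional extents were gamma with mean 20% and shape 0.6, 1.0 or 1.6, keeping subjects whose weighted extent was 10–40%. Baseline severity sums were 3 to 8. At follow-up a mean of 35% or 60% of the extent remained. Ranges are over the six combinations.

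| Response | Protocol conversion | Footnote conversion |
|---|---|---|
| EASI-50 | 30.2–76.2% | 45.7–86.7% |
| EASI-75 | 7.0–34.1% | 22.9–64.4% |
| EASI-90 | 1.1–8.3% | 11.8–43.2% |

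Across the three cut-offs, 9.5–36.7% of simulated subjects were reclassified upward and at most 0.9% downward. Mean baseline EASI fell from 10.8–11.2 to 9.0–9.8.

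**The case against.** The strongest reply is that this is a footnote to a listing shell and looks like a typing slip, not a scoring rule. The SAP text available gives neither the region multipliers nor the EASI formula, so a total cannot be computed from it alone. A programmer would have to go to Appendix C, where the correct area table sits beside the multipliers, and SAP section 2 refers readers to the protocol and eCRFs. EASI is a clinician assessment captured by eCOA, and the age 8 and over form has a field for the 0–6 region score, so the score may arrive without passing through this footnote.

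Most of this stands. It makes the consequence conditional, but it does not make the footnote right. The listing shows area as a percentage band, and if that is how it is stored, something must convert it. A single misread digit in the PDF text cannot be ruled out, but the missing 0% entry would remain, whereas the severity footnote on the same listing starts at its zero category.

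Two stronger readings are tempting. A reader might infer that the trial's EASI response rates are inflated; the documents do not show that any derivation uses the footnote, and Example 2 shows that the effect is not upward for every subject. A reader might also infer bias in favour of B244; the same conversion would apply to all three arms, and nothing in the documents shows a difference between arms.

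**Conclusion.** The footnote contradicts Protocol Appendix C on the 1–9% band, and no declared change explains it. It is an error in a stated conversion rule. If EASI were derived with it, a region at 1–9% would count as clear, and improvement and EASI-50/75/90 response would usually be overstated; 58% becoming 100% in Example 1 is exact arithmetic. The simulated ranges rest entirely on assumed distributions and support only the statement about usual direction.

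The reach is limited. The EASI endpoints are exploratory, and SAP 7.4 says their p-values are to be read as such. The primary WI-NRS ANCOVA does not use EASI; only the descriptive WI-NRS summaries by baseline EASI could shift. The point is worth correcting because reported responder rates could be materially wrong and a range check would not reveal it.

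**What to change.** In footnote 2 of Listing 16.2.6.6, add 0% = 0 and change 1–9% to 1; leave the five higher bands as they are. Then confirm that the eCOA system and the ADaM program compute EASI totals by Appendix C, for example by recalculating totals by hand for several subjects with at least one region at 1–9%. If the footnote's conversion turns out to have been used, rerun the EASI mean-change and responder tables, the addendum's EASI tables and the summaries by baseline EASI stratum. The cost is one footnote line and one derivation check; reruns are needed only if the check fails.

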1.3 APPENDIX C: Figures

| Display Number | Title | Population | Unique/Repeat |
|-----------------|------------------------------------|------------|---------------|
| Figure 14.2.1.1 | Daily WI-NRS Scores v Time | mITT | Unique |
| Figure 14.2.1.2 | Daily WI-NRS Scores v Time | PP | Repeat |
| Figure 14.2.1.3 | Weekly WI-NRS Scores v Time | mITT | Repeat |
| Figure 14.2.1.4 | Weekly WI-NRS Scores v Time | PP | Repeat |
| Figure 14.2.1.5 | WI-NRS Responder (4-Point | mITT | Unique |
| | Improvement) v Time | | |
| Figure 14.2.1.6 | WI-NRS Responder (4-Point | PP | Repeat |
| | Improvement) v Time | | |
| Figure 14.2.1.7 | WI-NRS Responder (Any | mITT | Unique |
| | Improvement) v Time | | |
| Figure 14.2.1.8 | WI-NRS Responder (Any | PP | Repeat |
| | Improvement) v Time | | |
| Figure 14.2.2.1 | Daily AI-NRS Scores v Time | mITT | Repeat |
| Figure 14.2.2.2 | Daily AI-NRS Scores v Time | РР | Repeat |
| Figure 14.2.2.3 | Weekly AI-NRS Scores v Time | mITT | Repeat |
| Figure 14.2.2.4 | Weekly AI-NRS Scores v Time | РР | Repeat |
| Figure 14.2.2.5 | AI-NRS Responder (4-Point | mITT | Repeat |
| | Improvement) v Time | | |
| Figure 14.2.2.6 | AI-NRS Responder (4-Point | PP | Repeat |
| | Improvement) v Time | | |
| Figure 14.2.2.7 | AI-NRS Responder (Any | mITT | Repeat |
| | Improvement) v Time | | |
| Figure 14.2.2.8 | AI-NRS Responder (Any | PP | Repeat |
| | Improvement) v Time | | |
| Figure 14.2.3.1 | IGA Score v Time | mITT | Unique |
| Figure 14.2.3.2 | IGA Score v Time | РР | Repeat |
| Figure 14.2.3.3 | IGA Responder (0 or 1 with 2-Point | mITT | Unique |
| | Improvement) v Time | | |
| Figure 14.2.3.4 | IGA Responder (0 or 1 with 2-Point | РР | Repeat |
| | Improvement) v Time | | |

| Figure 14.2.3.5 | IGA Responder (0 or 1) v Time | mITT | Repeat |
|-----------------|---------------------------------|------|--------|
| Figure 14.2.3.6 | IGA Responder (0 or 1) v Time | PP | Repeat |
| Figure 14.2.3.7 | IGA Responder (Any Improvement) | mITT | Repeat |
| | v Time | | |
| Figure 14.2.3.8 | IGA Responder (Any Improvement) | PP | Repeat |
| | v Time | | |
| Figure 14.2.4.1 | EASI Score v Time | mITT | Unique |
| Figure 14.2.4.2 | EASI Score v Time | PP | Repeat |
| Figure 14.2.4.3 | EASI-50 v Time | mITT | Unique |
| Figure 14.2.4.4 | EASI-50 v Time | PP | Repeat |
| Figure 14.2.4.5 | EASI-75 v Time | mITT | Repeat |
| Figure 14.2.4.6 | EASI-75 v Time | PP | Repeat |
| Figure 14.2.4.7 | EASI-90 v Time | mITT | Repeat |

A Phase II, Randomized, Double-Blind, Vehicle Controlled Study of the Efficacy, Safety, and Tolerability of B244 Topical Spray for the Treatment of Pruritus in Adults with a History of Atopic Dermatitis

Sponsor:

AOBiome, LLC [name]

ADDENDUM TO SAP v3.0

Version 1.0 22-Apr-22

ADDENDUM TO SAP REVIEW AND APPROVAL

This Addendum to Statistical Analysis Plan v3.0 (12Jan2022) has been prepared in accordance with team reviewers' specifications.

| Prepared by: [name]. Signing Reason: 1 am the author of this document Signing Time: 03 May 2022 4:44:40 AM PDT F18BA 1C2EF7C48A4B775BE54652AC840 | 03 May 2022 |
|--|------------------|
| [name], Bio-Statistician | Date |
| Sponsor Review: | 05 May 2022 |
| [name], Bio-Statistician | Date 05 May 2022 |
| [name], VP of Clinical Operations | Date |

ADDENDUM TO SAP v3.0

Version 1.0 22-Apr-22

Table of Contents

| 1 | Background and Purpose | . 4 |
|---|--|-----|
| 2 | Request 1: Worst Case Analysis | . 4 |
| 3 | Request 2: Intention-to-Treat Analysis | . 5 |
| 4 | List of Tables | . 6 |
| 5 | Table Shells | . 8 |

ADDENDUM TO SAP v3.0

Version 1.0 22-Apr-22

1 Background and Purpose

The purpose of this addendum to the final Statistical Analysis Plan (SAP) for the PRB244-01 study (v3.0 dated 12Jan2022) is to describe additional statistical analyses that will be performed in order to address requests by the FDA made on 27Mar2022. These requests are detailed in the sections below.

2 Request 1: Worst Case Analysis

FDA Request: You proposed the non-responder imputation analysis in which subjects who discontinue treatment early or who take on-treatment rescue medications will be imputed as a non-responder. Similar to the non-responder imputation analysis, we recommend that you provide additional analyses on the primary efficacy endpoint and relevant efficacy endpoints in which the underlying score-based variable values (e.g., WI-NRS, AI-NRS, IGA, etc.), are imputed with the worst score on/after date of first rescue medication use through the end of the study.

As a parallel to the non-responder imputation analysis, for score-based endpoints of WI-NRS, AI-NRS, IGA, and EASI, we will perform worst-value imputation on/after the date of first ontreatment rescue medication or date of subject early discontinuation through the end of the study. For this sensitivity analysis, all values on/after the date of first on-treatment rescue medication use or all values missing due to subject early discontinuation will be replaced with the worst value observed for each subject between first post-baseline assessment and first use of ontreatment rescue medication (WOCF). In the event there is no observation after baseline recorded, WOCF will be Baseline values.

Subjects who discontinue early should have (1) at least one treatment-emergent adverse event (TEAE) leading to discontinuation and (2) discontinuation occurring prior to their Week 4 visit in order to have their data imputed for WOCF analysis.

In cases where subjects completed the treatment period, but did not complete all of the follow-up period, the following logic will be used in order to fully parallel the NRI analysis. If subjects use rescue medications while on treatment and discontinue after the Week 4 visit, then only values from first on-treatment rescue medication use through last attended visit will be imputed with WOCF (i.e., missing data from visits that did not occur after Week 4 would not be imputed in this case).

The mITT population will be used for this analysis. For WOCF imputation of WI-NRS and AI-NRS values, the worst-observation would be the highest weekly average (not highest daily score) reported after baseline and before first on-treatment rescue medication use or before subject early discontinuation.

ADDENDUM TO SAP v3.0

Version 1.0 22-Apr-22

If a situation occurs where a visit is missed but a subsequent visit takes place for the same subject, then the missing data for that interim visit will not be imputed unless that visit occurs on/after the date of first on-treatment medication use.

3 Request 2: Intention-to-Treat Analysis

FDA Request: We recommend that you perform additional sensitivity analyses to include dropouts for whom no single score is collected and thus missing data handling strategies are to be considered. In this analysis, the analysis population will be the intent-to-treat (ITT) population.

To approximate an intent-to-treat population, LOCF methods will be applied for all randomized subjects missing Week 4 responses for endpoints (WI-NRS, AI-NRS, IGA, EASI, and responder analyses). Subjects missing Week 4 values will have their measurement imputed to be the LOCF value on treatment or baseline, whichever is later. Sensitivity analysis of WI-NRS, AI-NRS, IGA, EASI, and related responder analyses will be performed.

Intention-to-Treat Population (ITT): All subjects who were randomized, regardless of exposure to treatment.

For subjects who were randomized, but did not receive treatment, the baseline WI-NRS and AI-NRS scores will be calculated using the same approach that is used for treated subjects (as described in section 6.4 of the SAP), except that the reference date will be the date of the baseline visit instead of the date of first dose.

ADDENDUM TO SAP v3.0

Version 1.0 22-Apr-22

4 List of Tables

| Display Number | Title | Population | Unique/ | Request |
|----------------|---|------------|---------|---------|
| | | | Repeat | # |
| 14.2.2.2a | Mean Change in WI-NRS from Baseline to Week 4 – ANCOVA - WOCF | mITT | Repeat | 1 |
| 14.2.2.2b | Mean Change in WI-NRS from Baseline to Week 4 – ANCOVA – WOCF Sensitivity | mITT | Repeat | 1 |
| 14.2.2.2c | Mean Change in WI-NRS from Baseline to Week 4 – ANCOVA - LOCF | ITT | Repeat | 2 |
| 14.2.2.3.4a | Mean Change in WI-NRS from Baseline to Weeks 1 Through 8 - WOCF | mITT | Repeat | 1 |
| 14.2.2.3.4b | Mean Change in WI-NRS from Baseline to Weeks 1 Through 8 - WOCF Sensitivity | mITT | Repeat | 1 |
| 14.2.2.4.4a | Mean Change in AI-NRS from Baseline to Weeks 1 Through 8 - WOCF | mITT | Repeat | 1 |
| 14.2.2.4.4b | Mean Change in AI-NRS from Baseline to Weeks 1 Through 8 - WOCF Sensitivity | mITT | Repeat | 1 |
| 14.2.2.4.9 | Mean Change in AI-NRS from Baseline to Week 4 - LOCF | ITT | Repeat | 2 |
| 14.2.2.5.13 | Proportion of Subjects with ≥4 Point Improvement in WI-NRS from Baseline to Week 4 - LOCF | ITT | Repeat | 2 |
| 14.2.2.7.13 | Proportion of Subjects with ≥4 Point Improvement in AI-NRS from Baseline to Week 4 - LOCF | ITT | Repeat | 2 |
| 14.2.2.10.2a | Mean Change in EASI Total Score from Baseline to Weeks 2, 4, and 8 - WOCF | mITT | Repeat | 1 |
| 14.2.2.10.5 | Mean Change in EASI Total Score from Baseline to Week 4 - LOCF | ITT | Repeat | 2 |
| 14.2.2.11.2a | Mean Change in IGA from Baseline to Weeks 2, 4, and 8 - WOCF | mITT | Repeat | 1 |

ADDENDUM TO SAP v3.0

Version 1.0 22-Apr-22

| 14.2.2.11.5 | Mean Change in IGA from | ITT | Repeat | 2 |
|-------------|--|-----|--------|---|
| | Baseline to Week 4 - LOCF | | | |
| 14.2.2.14.7 | Proportion of Subjects with \geq 75% | ITT | Repeat | 2 |
| | Improvement in EASI (EASI-75) | | | |
| | from Baseline to Week 4 - LOCF | | | |
| 14.2.2.15.7 | Proportion of Subjects with $\geq 90\%$ | ITT | Repeat | 2 |
| | Improvement in EASI (EASI-90) | | | |
| | from Baseline to Week 4 - LOCF | | | |
| 14.2.2.16.7 | Proportion of Subjects with IGA of | ITT | Repeat | 2 |
| | Clear or Almost Clear and ≥ 2 Point | | _ | |
| | Improvement from Baseline to | | | |
| | Week 4 - LOCF | | | |
| 14.2.2.17.7 | Proportion of Subjects with IGA of | ITT | Repeat | 2 |
| | Clear or Almost Clear at Week 4 - | | | |
| | LOCF | | | |

Protocol: PRB244-01 Confidential ADDENDUM TO SAP v3.0

Version 1.0 22-Apr-22

5 Table Shells

| Tat Mean Change in WI-NRS from I (mIT | ble 14.2.2.2a Baseline to Week 4 – ANCO T Population) | VA – WOCF | |
|---|---|----------------|-------------|
| | B244 O.D. 5.0 | B244 O.D. 20.0 | Pooled B244 |

| Visit | Statistic Type | Statistic | (N=xx) | (N=xx) | (N=xx) | (N=xx) |
|----------------|----------------|----------------------|---------------|---------------|---------------|---------------|
| Week 4 CFB [1] | ANCOVA [2,3] | n | XX | XX | XX | XX |
| | | LSM (SE) [4] | xx.x (xx.xxx) | xx.x (xx.xxx) | xx.x (xx.xxx) | xx.x (xx.xxx) |
| | | 95% CI | (xx.x, xx.x) | (xx.x, xx.x) | (xx.x, xx.x) | (xx.x, xx.x) |
| | v. Vehicle | | | | | |
| | | LSM Difference (SE) | xx.x (xx.xxx) | xx.x (xx.xxx) | xx.x (xx.xxx) | N/A |
| | | 90% UCL Adjusted [5] | XX.X | XX.X | XX.X | N/A |
| | | p-value | X.XXXX | X.XXXX | X.XXXX | N/A |
| | 20.0 v 5.0 | _ | | | | |
| | | LSM Difference (SE) | N/A | xx.x (xx.xxx) | N/A | N/A |
| | | 90% UCL Adjusted | N/A | XX.X | N/A | N/A |
| | | p-value | N/A | X.XXXX | N/A | N/A |
| | | | | | | |

Note: WOCF = Worst Observation Carried Forward.

[1] CFB = Change from Baseline.

[2] ANCOVA = Analysis of Covariance model.

[3] Model contains treatment group and baseline WI-NRS as explanatory variables, where baseline WI-NRS = (Sum of daily WI-NRS scores from Day -7 to Day -1) / (Total number of WI-NRS diaries entered from Day -7 to Day -1) and at least one WI-NRS daily score is reported between Days -7 and -1. Multiplicity is adjusted for with the Dunnett Testing Method using a one-sided familywise error rate of 0.10. All subjects who meet mITT criteria are included. Data collected from the week of first on-treatment rescue medication use through the end of the study and missing data due to subject dropout will be imputed using WOCF. Data collected prior to the week of first on-treatment rescue medication use or dropout will be included.

[4] LSM = Least Squares Mean. SE = Standard Error.

[5] UCL = Upper Confidence Limit for one-sided confidence interval.

Source: Listing XXXX

PROGRAM NAME: XXXXXXXXXX

DATE: HH:MM/DDMMMYYYY

Vehicle

Programming Note:

٠

Repeat for 14.2.2.2b Mean Change in WI-NRS from Baseline to Week 4 - ANCOVA - WOCF Sensitivity for mITT Population

• Footnote [3] will be same as in 14.2.2.2a, except changing "one WI-NRS daily score is" to "four WI-NRS daily scores are"

Protocol: PRB244-01 Confidential ADDENDUM TO SAP v3.0

Version 1.0 22-Apr-22

- Repeat for 14.2.2.2e Mean Change in WI-NRS from Baseline to Week 4 ANCOVA LOCF for ITT Population
 - Add new footnote "Note: LOCF = Last Observation Carried Forward." as the first footnote.
 - Footnote [3] will be "Model contains treatment group and baseline WI-NRS as explanatory variables, where baseline WI-NRS = (Sum of daily WI-NRS scores from Day -7 to Day -1) / (Total number of WI-NRS diaries entered from Day -7 to Day -1) and at least one WI-NRS daily score is reported between Days -7 and -1. Multiplicity is adjusted for with the Dunnett Testing Method using a one-sided familywise error rate of 0.10. All subjects who meet ITT criteria are included and no data is excluded based on rescue medication use. Any values missing at Week 4 will be imputed using LOCF."

Protocol: PRB244-01 Confidential

ADDENDUM TO SAP v3.0

Version 1.0 22-Apr-22

Table 14.2.2.3.4a Mean Change in WI-NRS from Baseline to Weeks 1 Through 8 – WOCF (mITT Population)

| Visit | Statistic Type | Statistic | B244 O.D. 5.0 (N=xx) | B244 O.D. 20.0 (N=xx) | Pooled B244 (N=xx) | Vehicle (N=xx) |
|------------------------|----------------|--|-------------------------------------|-------------------------------------|-------------------------------------|-------------------------------------|
| Week 1 CFB [1] | MMRM [2,3] | n LSM (SE) [4] 95% CI | xx xx.x (xx.xxx) (xx.x, xx.x) | xx xx.x (xx.xxx) (xx.x, xx.x) | xx xx.x (xx.xxx) (xx.x, xx.x) | xx xx.x (xx.xxx) (xx.x, xx.x) |
| | v. Vehicle | LSM Difference (SE) 95% CI p-value | xx.x (xx.xxx) xx.x x.xxxx | xx.x (xx.xxx) xx.x x.xxxx | xx.x (xx.xxx) xx.x x.xxxx | N/A N/A N/A |
| Repeat for Weeks 2 – 8 | 20.0 v 5.0 | LSM Difference (SE) 95% CI p-value | N/A N/A N/A | x.xxxx xx.x (xx.xxx) xx.x | N/A N/A N/A | N/A N/A N/A |

Note: WOCF = Worst Observation Carried Forward.

[1] CFB = Change from Baseline.

[2] MMRM = Mixed Model Repeated Measures.

[3] Model uses a compound symmetry covariance structure and contains visit, treatment group, visit-by-treatment interaction, and baseline WI-NRS as explanatory variables, where baseline WI-NRS = (Sum of daily WI-NRS scores from Day -7 to Day -1) / (Total number of WI-NRS diaries entered from Day -7 to Day -1) and at least one WI-NRS daily score is reported between Days -7 and -1 and for the corresponding week. All subjects who meet mITT criteria are included. Data collected from the week of first on-treatment rescue medication use through the end of the study and missing data due to subject dropout will be imputed using WOCF. Data collected prior to the week of first on-treatment rescue medication use or dropout will be included.

[4] LSM = Least Squares Mean. SE = Standard Error. Source: Listing XXXX

PROGRAM NAME: XXXXXXXXXX

DATE: HH:MM/DDMMMYYYY

Programming Note:

- Repeat for 14.2.2.3.4b Mean Change in WI-NRS from Baseline to Weeks 1 Through 8 WOCF Sensitivity for mITT Population
 - Footnote [3] will be same as in 14.2.2.3.4a, except changing "one WI-NRS daily score is" to "four WI-NRS daily scores are"
- Repeat for 14.2.2.4.4 Mean Change in AI-NRS from Baseline to Weeks 1 Through 8 WOCF for mITT Population
 o Footnote [3] will be same as in 14.2.2.3.4a, except changing "WI-NRS" to "AI-NRS"
- Repeat for 14.2.2.4.4b Mean Change in AI-NRS from Baseline to Weeks 1 Through 8 WOCF Sensitivity for mITT Population

Protocol: PRB244-01 Confidential

ADDENDUM TO SAP v3.0

Version 1.0 22-Apr-22

- Footnote [3] will be same as in 14.2.2.3.4b, except changing "WI-NRS" to "AI-NRS"
- Repeat for 14.2.2.4.9 Mean Change in AI-NRS from Baseline to Week 4 LOCF for ITT Population
 - First column will contain only "Week 4 CFB [1]"
 - Add new footnote "Note: LOCF = Last Observation Carried Forward." as the first footnote.
 - Footnote [3] will be "Model uses a compound symmetry covariance structure and contains treatment group and baseline AI-NRS as explanatory variables, where baseline AI-NRS = (Sum of daily AI-NRS scores from Day -7 to Day -1) / (Total number of AI-NRS diaries entered from Day -7 to Day -1) and at least one AI-NRS daily score is reported between Days -7 and -1 and for the corresponding week. All subjects who meet ITT criteria are included and no data is excluded based on rescue medication use. Any values missing at Week 4 will be imputed using LOCF."

Protocol: PRB244-01 Confidential

ADDENDUM TO SAP v3.0

Version 1.0 22-Apr-22

Table 14.2.2.5.13 Proportion of Subjects with ≥4 Point Improvement in WI-NRS from Baseline to Week 4 – LOCF (ITT Population)

| Visit | Statistic Type | Statistic | B244 O.D. 5.0 (N=xx) | B244 O.D. 20.0 (N=xx) | Pooled B244 (N=xx) | Vehicle (N=xx) |
|--------|----------------|----------------------------------|------------------------------|------------------------------|------------------------------|------------------------------|
| Week 4 | Logistic [1,2] | n/N (Proportion %) [3] 95% CI | xx/xx (xx.x) (xx.x, xx.x) | xx/xx (xx.x) (xx.x, xx.x) | xx/xx (xx.x) (xx.x, xx.x) | xx/xx (xx.x) (xx.x, xx.x) |
| | v. Vehicle | Odds Ratio (95% CI) p-value | x.xx (x.xx, x.xx) x.xxxx | x.xx (x.xx, x.xx) x.xxxx | x.xx (x.xx, x.xx) x.xxxx | N/A N/A |
| | 20.0 v 5.0 | Odds Ratio (95% CI) p-value | N/A N/A | x.xx (x.xx, x.xx) x.xxxx | N/A N/A | N/A N/A |

Note: LOCF = Last Observation Carried Forward.

[1] Logistic regression model contains treatment group as the explanatory variable. At least one WI-NRS daily score is reported between Days -7 and -1 and for the corresponding week. All subjects who meet ITT criteria are included and no data is excluded based on rescue medication use. Any values missing at Week 4 will be imputed using LOCF. [2] Treatment response is improvement by \geq 4 Points in WI-NRS score (i.e., decrease in WI-NRS score by at least 4 points from Baseline to Post-Baseline visit).

[3] n is the number of subjects who have improved at that visit. N is the number of subjects with data at that visit, regardless of improvement status.

Source: Listing XXXX

PROGRAM NAME: XXXXXXXXXX

